3.2 Randomization

A blocked randomization scheme with a block size of 4 (ratio of 3:1 of active:placebo) that is stratified by site will be used. Site-specific randomization lists will be provided to the Production manager (unblinded personnel) prior to any subjects being randomized.

For each subject, at Visit 3, one week before bone marrow aspiration (BMA), the clinical site will notify the cell culture facility of the eligibility of a subject; the cell production facility personnel will then sequentially assign a randomization number according to the randomization list for each site.

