5 Blood Biochemistry: Na, K, Cl, HCO₃, BUN, Cr, Glucose, Ca, Mg, Phosphorus, total protein, triglycerides (TG), Total cholesterol, HDL, LDL, urea, creatinine, total bilirubin, AST(GOT), ALT(GPT), ALP - Time Window: +/- 2 hours

6 Urinalysis (dip-stick test) - Specific Gravity, pH, glucose, protein, ketones, blood

7 Coagulation PT, PTT

8 Can be done prior to discharge

4. Study Treatment

The investigational products for this study will be

- MSC-NTF cells
- Placebo (Dulbecco Modified Eagle Medium, DMEM)

IT Transplant Procedure: Participants will undergo a lumbar puncture (Spinal needle 20GA 3.50 IN (0.9 x 90 mm)) followed by intrathecal injection of cells or placebo (DMEM).

IM Transplant Procedure: Participants will undergo a unilateral (right) IM transplantation of cells or placebo solution (DMEM) into 24 sites in the upper arm.

The study flowchart described above is shown in Figure 2.

[figure not shown]

Figure 2: Study Groups Flowchart

5. Sample Size

This is a Phase II study for which no formal sample size calculation has been performed. The sample size chosen was not based on statistical considerations. The total of 36 treatment and 12 placebo subjects are expected to be a sufficient number to obtain adequate characterization of common treatment emergent adverse events and to observe trends for treatment effects on the efficacy measures chosen for this study. Additionally, with 36 subjects in the MSC-NTF treatment group, the study has 95% probability of seeing adverse events that occur at a true rate of 8% or greater. Therefore, if an adverse event of a specific type does not occur, there is 95% probability that the true rate of the adverse event is less than 8%.

6. Analysis Populations

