7.2 Efficacy Endpoints

The efficacy endpoints are the following:

- Revised ALS Functional Rating Scale (ALSFRS-R)
- Slow Vital Capacity (SVC) (as a percent of normal)

[REDACTED]

[REDACTED]

[REDACTED]

[REDACTED]

[REDACTED]

[REDACTED]

8. General Considerations

Summaries for continuous variables will include the sample size, mean, standard deviation, median, minimum, and maximum. Minima and maxima will be reported with the same precision as the raw values; means, standard deviations, and medians will be presented to one additional decimal place than reported in the raw values. Summaries for discrete variables will include frequencies and percentages. All percentages will be rounded to one decimal place (i.e., XX.X%). Differences between treatment groups will be calculated as active – placebo and change from Baseline will be calculated as post-treatment – pre-treatment (OR follow-up visit – Baseline). The Baseline value will be defined as the last non-missing measure prior to initiation of investigational treatment. Additionally, for the pre-transplantation period and Transplantation Visits, change from screening summaries will be calculated as pre-transplantation period/Transplantation Visit minus screening.

All efficacy analyses will use one-sided alpha = 0.10 tests (which corresponds to a 2-sided alpha=0.20 test). The two-sided 80% lower confidence limit will be presented for which the lower bound is the 1-sided 90% confidence limit. In addition, the two-sided 90% and 95% confidence intervals around the difference between treatments as well as two-sided 95% confidence intervals around the point estimates within each treatment group will be provided. All summaries will be presented by treatment.

Statistical programming and analyses will be performed using SAS® Version 9.2 or higher.

[REDACTED]

[REDACTED]

[REDACTED]

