Descriptive statistics on the observed and change from baseline in the ALSFRS-R total score, ALSFRS-R motor score, and SVC will be summarized at each visit, by treatment group. The analyses will be evaluated for the FAS primarily based on available data (no imputation). Figures presenting the mean ALSFRS-R total and motor scores and SVC score over time by treatment group will be presented. Additionally, figures presenting the ALSFRS-R total and motor scores over time, as separate line plots for each subject will be generated. The change from the Screening Visit measure will be summarized for measures during pre-transplantation. The change from Baseline measure will be summarized for measures post-transplantation. The pre-transplantation slope (change in score per month calculated as the difference between the visit date minus the screening date divided by 30.4375) will be estimated from visits prior to transplantation (including the measure pre-transplantation at the transplantation visit). The post-transplantation slope (change in score per month calculated as the difference between the visit date minus the transplantation date divided by 30.4375) will be estimated from visits post transplantation (including the measure pre-transplantation at the transplantation visit). The analysis of change in slope from pre-transplantation to post-transplantation in ALSFRS-R total and motor and in SVC will be estimated using a two-step model. In the first step, linear regressions will be fitted to each subject's pre-transplantation and post-transplantation data separately; and in the 2nd step, the slopes (pre- and post-transplantation slopes) from the first step will be used as a response variable and treatment, period (0 for pre-transplantation slope and 1 for post-transplantation slope), and treatment by period interaction as explanatory variables in a fixed-effects linear model. The two-way interaction between treatment and period will be used to compare the change in slope

in the active treatment group to the change in slope in the placebo group. The post - pre slope estimate within each treatment group will be used to test the change from pre-transplantation to post-transplantation.

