The slopes, pre- and post- transplantation and the difference in slopes pre- and post-transplantation will be tested for normality using the Kolmogorov-Smirnov statistic. If the slopes deviate from normality additional summaries will be presented using a Wilcoxon Rank-Sum test on the slope estimates obtained from the mixed-effects linear model. The above analysis is based upon all data from screening through Week 24 and similar analysis will be repeated through 8-week, 12-week, 16-week follow-up periods for ALSFRS and through 8-week and 16-week follow-up periods for SVC.

To assess the robustness of the analysis results when warranted, the two-step model will be repeated with missing values imputed using multiple imputation methods. The monotone regression method will be performed using the SAS procedure PROC MI.

Note, that repeating the imputation 30 times allows for a better understanding of the additional variability inherent in imputing missing values. ALSFRS-R motor scores will be calculated similarly. The 30 sets each of total and motor ALSFRS-R scores will then be analyzed by standard SAS mixed modeling method as specified earlier. [REDACTED]

The procedure for imputing for SVC is analogous to ALSFRS-R. Again, 30 complete datasets will be generated and the Linear Mixed Model to analyze SVC will be fitted on each of the 30 datasets and the results combined to give yield overall inference.

Each subject's pre and post-treatment slope, standard error, and p-value testing the slope versus 0 will be presented in a listing. Additionally, the percent change in slope (post – pre)/absolute(pre) will be calculated and listed. The frequency and percentage of subjects with at least a 10%, 15%, 20%, 25%, and 30% change (improvement) in slope will be summarized and tested between the treatment groups using Fisher's Exact test. These analyses will be performed for subjects showing improvements in ALSFRS-R, SVC, ALSFRS-R and SVC, ALSFRS-R or SVC over the 8-week, 16-week and 24-week post-transplantation follow-up periods.

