showing changes in suicide ideation scores from screening (lifetime measure) to worst on Baseline (pre-transplantation period) and from Baseline to worst post-treatment will also be provided. Data will be reported as available without data imputation.

12. Interim Analyses

There are no interim analyses planned for this study.

13. Deviations from Protocol-Stated Analyses

- [REDACTED]
- [REDACTED]
- [REDACTED]
- Updated mixed linear repeated measures statistical model to be a simple linear regression along with general linear model to compare changes in slopes between treatment groups as described above.
- Added slope analysis for 8-week and 16-week follow-up periods was added for the efficacy endpoints.
- Changed population definitions from the protocol stated definitions by removing analyses on mFAS and PP populations.
- Protocol referred to day of transplantation as Day 0, however in the SAP it is treated as Day 1.
- Changes between the original protocol and Amendment 1 are assumed to not impact any statistical analyses

14. Reporting Conventions

Reporting conventions will adhere when possible to the International Conference on Harmonization (ICH) Guidance E3, "Structure and Content of Clinical Study Reports". All tables and listings will be presented in landscape format. All SAS output for tables and listings will be distributed in PDF files.

15. References

16. SAP Revision History

Section #	Description of Change	Rationale
6	Updated FAS definition and removed mFAS	During the blinded data review it was determined that the difference between the FAS and mFAS was only one subject and hence no analyses would be performed on the mFAS

Section #	Description of Change	Rationale
6	Analysis on PP population is deleted	Due to the small sample size in the study, the 3:1 ratio of randomization between active and placebo and the possibility that a disproportionate number of the subjects may be in the Placebo group, analysis on the PP population will not be performed.
10.2 and 10.3.1	Updated the primary model from mixed-effects linear model to two-step model.	The mixed-effects linear model has restriction on the random effects estimates (slope) which causes the estimated slopes to be either lower or higher than the actual slopes from simple linear regression which was deemed to be more appropriate.

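### Step 2 of the slope analysis has one residual variance by default with arms of 36 and 12, so the between-arm test and its limits can be off-nominal when the arms differ in slope variability

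*SAP*

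**What the plan says.** SAP 10.2 fits a straight line to each patient's pre-transplantation data and another to the post-transplantation data. The two slopes per patient are then the responses, with treatment, period and "treatment by period interaction as explanatory variables in a fixed-effects linear model". On the between-arm comparison it says: "The two-way interaction between treatment and period will be used to compare the change in slope" in the active arm with that in placebo. SAP section 13 describes the change from the protocol this way: "Updated mixed linear repeated measures statistical model to be a simple linear regression along with general linear model to compare changes in slopes".

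SAP section 5 gives the arm sizes ("The total of 36 treatment and 12 placebo subjects"), and section 3.2 gives 3:1 allocation in blocks of four, stratified by site. SAP section 8 sets a one-sided 0.10 level for all efficacy tests. It asks for an 80% interval, whose lower bound is the one-sided 90% limit, and for "the two-sided 90% and 95% confidence intervals around the difference between treatments".

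Neither document mentions arm-specific variances, Welch or Satterthwaite degrees of freedom, or a robust standard error for this model. The only fallback, in SAP 10.2, is a rank-sum test offered as an additional summary when slopes look non-normal. Unequal spread does not trigger it. The SAP does not state the common residual variance; it is the default of the model class named.

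**The concern.** With 3:1 allocation, a pooled variance is estimated mostly from the arm that matters least to the precision of the contrast. The treated arm supplies 35 of the 46 pooled degrees of freedom for per-patient change (76%). With equal variances, the placebo arm supplies (1/12)/(1/36 + 1/12) = 75% of the contrast's sampling variance. If the arms differ in spread, the model's standard error is therefore off: too large when treated patients vary more, too small when placebo patients do.

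At stake are the between-arm test and its 80%, 90% and 95% limits for ALSFRS-R and SVC, which are the trial's randomised efficacy result.

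**Working it through.** **Inputs.** From the SAP: arms of 36 and 12 (section 5), one-sided 0.10 (section 8), the step 2 model (10.2). Assumed, because the documents give no slope SD by arm or period: normal slopes, all 48 patients with both slopes, the variance ratios below, and pre/post correlations (rho) of 0 to 0.7.

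**The plan's own figure.** One-sided 0.10 and two-sided 0.20 share the normal critical value 1.2816, so the SAP's equivalence is right. Simulating step 2 as written (96 slopes, 92 df) with equal variances and rho = 0 gives size 0.099–0.100 and 95% coverage 0.950–0.951. The nominal level holds under the model's own assumptions.

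**Formulas, per-patient change in slope.** With change variances vT (treated) and vC (placebo):
- pooled SE² = [(35 vT + 11 vC)/46] × (1/36 + 1/12)
- true SE² = vT/36 + vC/12

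**Doubling one arm's post-slope variance.** Randomisation is at Visit 3, before treatment (Protocol 6.3.4), so pre-slope variances are equal in expectation. Set them to 1. An arm with post variance 1 has change variance 2 − 2 rho. An arm with post variance 2 has 3 − 2 rho √2. The ratio is 1.5 at rho = 0 and 1.02/0.60 = 1.7 at rho = 0.7. At rho = 0:
- Treated doubled (vT = 3, vC = 2): pooled (127/46) × 0.1111 = 0.3068; true 3/36 + 2/12 = 0.2500; SE ratio √1.227 = 1.108.
- Placebo doubled (vT = 2, vC = 3): pooled (103/46) × 0.1111 = 0.2488; true 2/36 + 3/12 = 0.3056; SE ratio √0.814 = 0.902.

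**A two-fold ratio in the variance of change itself.**
- vT:vC = 2:1: (81/46) × 0.1111 = 0.1957 against 0.1389; SE ratio 1.187.
- vT:vC = 1:2: (57/46) × 0.1111 = 0.1377 against 0.1944; SE ratio 0.841.

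At rho = 0 this needs a three-fold ratio in post-slope variance, since (1 + 3)/(1 + 1) = 2.

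**Simulated one-sided size, pooled test on change (nominal 0.10).**

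| Case | Size | 95% coverage |
|---|---|---|
| Equal variances | 0.10 | 0.95 |
| Treated post variance ×2, rho 0 to 0.7 | 0.078 to 0.072 | 0.97 |
| Placebo post variance ×2, rho 0 to 0.7 | about 0.125 (0.12–0.13) | 0.926 at a change ratio of 1.5 |
| Change variance 2:1, treated larger | 0.065 | 0.98 |
| Change variance 2:1, placebo larger | 0.14 | 0.90 |

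With arm-specific variances and Satterthwaite df, size was 0.098–0.102 and coverage 0.948–0.951 throughout.

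**Power** at an effect of 0.7 SD of placebo change. With treated post variance doubled, pooling loses about 4–6 points. With treated change variance doubled, power is 63% pooled against 71–72% with arm-specific variances.

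**Step 2 as literally written.** No subject term is listed, so a patient's two slopes count as independent. With equal variances the model's SE exceeds the true SE by a factor of 1/√(1 − rho): 1.195, 1.414 and 1.826 at rho 0.3, 0.5 and 0.7. Size is then 0.063, 0.036 and 0.010. With placebo post variance doubled, it is 0.086, 0.055 and 0.024 at the same correlations. If placebo slopes have twice the variance in both periods and rho = 0.3, the two errors cancel (size 0.100, coverage 0.949).

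**The case against.** The strongest reply has four parts.

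- **The error rates belong to a different test.** A reader might infer that the SAP's analysis has a 14% false-positive rate, or that its size is wrong whenever the variances differ. Neither follows. The 0.14 is for a pooled test on per-patient change, which matches step 2 as written only at zero pre/post correlation. With positive correlation the written test is often conservative, and the errors can cancel. This stands. But the cancellation is accidental: when treated patients vary more, both errors point the same way, and adding a subject term alone would leave the variance problem exposed.
- **Nothing in the plan says the variances differ.** A reader might take the responder cut-offs in SAP 10.2 (10% to 30% improvement in slope) as supposing that only some treated patients respond, hence a wider treated distribution. They suppose no such thing. They count patients in both arms above fixed cut-offs, which can be done under a uniform shift. This stands, so the ratio remains an assumption.
- **The false-positive direction lacks a mechanism.** If treatment affects no patient, post-slope variances are equal in expectation and pooling does no harm to size. This also stands. The practical concern is then power and interval coverage when there is an effect.
- **Stakes and convention.** Efficacy is secondary, the sample was not sized for it, and a pooled variance is conventional. The mixed model in Protocol 6.9.4.3 named no arm-specific covariance either. That limits the weight of the point but does not answer it, given how little the remedy costs.

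**Conclusion.** The point holds in a limited form. Step 2 has one residual variance by default with arms of 36 and 12, and nothing in the SAP guards against unequal spread, so the between-arm test and limits can be off-nominal when the arms differ. For a doubling of one arm's post-slope variance, the pooled test on change has size of about 0.07–0.08 or about 0.125 instead of 0.10. For a two-fold ratio in the variance of change it is about 0.065 or 0.14.

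These figures rest on assumed ratios, normal slopes and complete data. The documents do not show that the variances differ, or in which direction. In the model as written, the missing subject term can be the larger error, so the two should be repaired together. This is a cheap improvement in robustness, not a demonstrated inflation of the trial's error rate.

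**What to change.** In SAP 10.2, make each patient's change in slope (post minus pre) the response and compare it by treatment with arm-specific variances and Satterthwaite (Welch) degrees of freedom, for example PROC MIXED with REPEATED / GROUP=treatment. Use that standard error for the 80%, 90% and 95% between-arm intervals and for the multiply imputed repeats. Report the pooled-variance result as a sensitivity analysis. This settles the pairing of the two slopes and the variance assumption in one step.

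**Cost.** One SAP sentence and one procedure option. If the variances are equal, degrees of freedom fall from 46 to about 19, and power at a 0.7 SD effect falls by about 1 percentage point (78.7% to 77.9%). The subgroup repeats in SAP 10.2.1 would lose roughly 2–3 points (assumed sizes 18 v 6 down to 9 v 3), so the pooled variance may be retained there if the SAP says so.

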6.9.4.3. Efficacy Analyses

Secondary Objectives: The change in slope between the treatment and placebo group and from pre-transplantation to post-transplantation in ALSFRS-R and in SVC (as a percent of normal for age and sex) will be estimated using the mixed linear statistical model.

The fixed effect variables in the model will be:

- Visit, expressed in days from the beginning of treatment (i.e. pre-treatment times will have negative values, post-treatment times positive values).
- Treatment
- Two-way interactions between visit & post-treatment indicator, (0 for pre-treatment visits, 1 for post-treatment visits) and visit & treatment
- Three-way interaction between visit & post-treatment visit indicator & treatment
- Site

The repeated measures within a subject over visit will also be accounted for in the model, wherein, the covariance structure will be evaluated using Bayesian information criterion (BIC). Covariance structures to be evaluated are: unstructured, toeplitz, spatial power with day, and compound symmetry.

The three-way interaction between visit & post-treatment visit indicator & treatment will be used to compare the change in slope in the treatment group to the change in slope in the placebo group.

The post-pre slope estimate within each treatment group will be used to test the change from pre-transplantation to post-transplantation.

Repeated measures covariance will be estimated by restricted maximum likelihood. The Kenward and Roger method will be used to determine degrees of freedom and compute p-values.

Secondary objectives will be evaluated for the FAS, as well as the PP populations.

Exploratory Objectives: The analysis for EIM (optional) and HHD will employ the same modeling approach as described above for the secondary objectives. The analysis for HHD will be based on a combined score reflecting muscles in the right arm.

A further analysis of HHD will compare the score for the right arm to the score for the left arm. The linear mixed model will include, in addition to the terms described above, an indicator for "right arm", interactions between that indicator and all other variables in the model, and a random effect term for the right arm indicator. Therefore, the fixed effect variables in the model will be:

- Visit, expressed in days from the beginning of treatment (i.e. pre-treatment times will have negative values, post-treatment times positive values);
- Treatment;
- Right arm indicator;

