2.2 Secondary Objectives

The secondary objectives of this study are

- To compare the change in slopes from the pre-transplantation period to the post-transplantation period in ALSFRS-R between the treatment and placebo groups through 12 and 24 weeks post-transplantation.
- To compare the change in slopes from the pre-transplantation period to the post-transplantation period in SVC between the treatment and placebo groups through 12 and 24 weeks post-transplantation.
- To compare the slope of the rate of decline in the ALSFRS-R at 12 and 24 weeks following transplantation relative to the 12-16 week Baseline period before transplantation in all patients (both treatment and placebo groups).
- To compare the slope of the rate of decline in SVC at 12 and 24 weeks following transplantation relative to the 12-16 week Baseline period before transplantation in all patients (both treatment and placebo groups).

[REDACTED]

[REDACTED]

- [REDACTED]
- [REDACTED]
- [REDACTED]
- [REDACTED]
- [REDACTED]
- [REDACTED]
- [REDACTED]

3. Study Design and Procedures

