10.2.1 Subgroup analyses

Subgroup analyses will be performed to investigate the consistency of the treatment effects for different groups of subjects.

Subgroup analyses will be conducted for the following endpoints:

- ALSFRS-R total score
- ALSFRS-R motor score
- SVC

Subgroups to be evaluated include the following:

- Baseline SVC:
 - $\geq 70\%$
- Baseline ALSFRS-R total score:
 - < -2 in the change from screening to baseline in ALSFRS-R total score
 - ≥ -2 in the change from screening to baseline in ALSFRS-R total score
- Baseline ALSFRS-R motor score:
 - < -1 in the change from screening to baseline in ALSFRS-R motor score
 - ≥ -1 in the change from screening to baseline in ALSFRS-R motor score

The primary analysis model will be repeated for each level of the subgroups.

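### The between-arm comparison of change in slope should adjust for pre-transplantation slope and site; as worded it does neither, and main-effect covariates from SAP 10.2.2 cannot move its estimate

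*SAP*

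**What the plan says.** SAP 10.2 fits one straight line to each patient's pre-transplantation scores and another to the post-transplantation scores. Both slopes become responses in a fixed-effects linear model whose only terms are treatment, period and treatment by period. For the between-arm question: "The two-way interaction between treatment and period will be used to compare the change in slope" in the two arms. Both lines are defined as "including the measure pre-transplantation at the transplantation visit", so one reading enters both slopes.

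The same model serves the within-arm question: "The post - pre slope estimate within each treatment group will be used to test the change". That answers a separate secondary objective in SAP 2.2: "To compare the slope of the rate of decline in the ALSFRS-R at 12 and 24 weeks following transplantation" against the baseline period.

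On site, SAP 3.2 describes a blocked 3:1 scheme "that is stratified by site will be used". Protocol 6.9.4.3, under "The fixed effect variables in the model will be", lists site. The SAP's second step does not, and the legible entries in SAP section 13 declare the change of model but not the loss of site.

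The model is reused elsewhere: "similar analysis will be repeated through 8-week, 12-week, 16-week follow-up periods for ALSFRS"; and in SAP 10.2.1, "The primary analysis model will be repeated for each level of the subgroups". SAP 10.2.2 adds covariates to it one at a time and then builds a multivariable model. It names neither pre-slope nor site, and does not say whether covariate-by-period terms are meant.

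**The concern.** A pre-slope from four visits over 12 to 16 weeks is a noisy measurement. As an outcome row it passes all of that noise into the treatment effect. As a covariate it would remove variance from the post-slope. The shared transplantation-visit value makes matters worse: an error in it tilts the two lines in opposite directions and inflates the apparent change. That reading comes after randomisation at Visit 3 but before treatment, so the pre-slope is still a legitimate pre-treatment covariate.

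The comparison has 12 placebo patients and is meant to show trends (SAP section 5), so avoidable variance matters. The covariate step has its own problem: it can produce a model that looks adjusted, with a different p-value, while the treatment estimate has not been adjusted at all.

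**Working it through.** **Plan's own figures.** There is none for efficacy. The only design probability, 95% for an adverse event at an 8% rate, reproduces (1 − 0.92^36 = 0.950) but does not bear on this point.

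**Inputs from the documents.** 36 active and 12 placebo; one-sided alpha 0.10; three sites. ALSFRS-R after treatment at weeks 0, 2, 4, 8, 12, 16, 20, 24; SVC without weeks 12 and 20, which are telephone contacts. Pre-visits taken at weeks 0, 5, 9, 14, within the scheduled windows.

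**Assumed, because not given.** Base case: true slope SD 0.8 points/month in each period, correlation 0.8 between true pre- and post-slopes, residual SD 1.5 points, effect 0.5 points/month. The effect is about half of the 0.92 points/month decline cited in Protocol 6.3.7 (0.5/0.92 = 0.54).

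**Step 1: error of each slope.** The error variance of a fitted slope is (residual variance)/S, where S is the sum of squared deviations of visit times from their mean. Pre-period: deviations −7, −2, 2, 7 weeks, so S = 106. Post-period at Week 24: S = 535.5, so the pre-slope error variance is 535.5/106 = 5.05 times the post-slope's (535.5/136 = 3.94 for a 16-week pre-period, 535.5/80 = 6.69 for 12 weeks). For SVC it is 430/106 = 4.06.

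**Step 2: variances at Week 24, base case.** One month is 30.4375 days, so 1 week² = (7/30.4375)² = 0.05289 month².
- Var(pre) = 0.64 + 2.25/(106 × 0.05289) = 0.64 + 0.401 = 1.041
- Var(post) = 0.64 + 2.25/(535.5 × 0.05289) = 0.64 + 0.079 = 0.719
- Covariance from the shared reading = 2.25 × (7/106) × (−10.75/535.5)/0.05289 = −0.056
- Cov(pre, post) = 0.8 × 0.64 − 0.056 = 0.456
- Var(change) = 1.041 + 0.719 − 2 × 0.456 = 0.850 (rounded after summing)
- Var(post given pre) = 0.719 − 0.456²/1.041 = 0.520
- Ratio = 0.850/0.520 = 1.63

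With 1/36 + 1/12 = 0.111, the SEs are √(0.850 × 0.111) = 0.31 and √(0.520 × 0.111) = 0.24. Without the shared reading, Var(change) would be 0.850 − 2 × 0.056 = 0.737, so it adds 15%. At Week 8 it adds 30%.

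**Step 3: other windows.** The range covers slope SD 0.5–1.0, correlation 0.5–0.95 and residual SD 0.5–2.

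| ALSFRS-R window | S (post) | Pre/post error variance | Var(change)/Var(adjusted), base case | Range |
|---|---|---|---|---|
| Week 24 | 535.5 | 5.05 | 1.63 | 1.06–3.3 |
| Week 16 | 190 | 1.79 | 1.55 | 1.06–2.7 |
| Week 12 | 92.8 | 0.88 | 1.46 | 1.06–2.3 |
| Week 8 | 35 | 0.33 | 1.35 | 1.05–1.8 |

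The adjusted estimator had the smaller variance at every point of the range.

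**Step 4: power by simulation** (three sites of 12:4; paired change test against the model adjusted for pre-slope).

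| Case | Change test | Adjusted |
|---|---|---|
| Base, Week 24 | 62% | 77% |
| Base, Week 8 | 37% | 42% |
| Correlation 0.5, Week 24 | 52% | 70% |
| Slope SD 1.0, residual SD 1, Week 24 | 70% | 76% |
| Slope SD 1.0, correlation 0.95, residual SD 0.5, Week 24 | 99.2% | 99.4% |

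Type I error of the adjusted test was 10.3%. Adding site when there is no true site effect moved power from 77.0% to 76.9%. Read literally, the two-row model has no patient term and gives 41%. That is a separate defect and is not counted in the gain.

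**Step 5: covariates in the two-row model.** With complete pairs, the interaction column, after removing intercept, treatment and period, is (T − mean T)(period − ½). For each patient its two values sum to zero, so it is orthogonal to anything constant within a patient, including site. The interaction estimate therefore cannot move. In the base case the reported SE nevertheless falls from 0.44 to 0.39. Simulated with a covariate correlated 0.6 with the true pre-slope, the mean shift was 0.000 with complete pairs, 0.015 with one post-slope missing and 0.039 with five. The same covariate moves the one-record estimate by about 0.05–0.06.

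**Step 6: within-arm test.** In the base case the paired test of slope change in the active arm had 10.0% type I error. A within-arm test taken from the adjusted model with centred pre-slope had 14.8%, because that model treats the mean pre-slope as fixed.

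**The case against.** The strongest reply is that the SAP does what its objective asks. The objective is a comparison of change in slopes, the protocol's three-way interaction is also a difference of differences, and the switch of model is declared. The estimator is unbiased, efficacy is secondary and no power is claimed. All of that is true. It makes this an efficiency point, but the adjusted model estimates the same between-arm effect under randomisation.

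Second, the change in SE and p-value in Step 5 depends on the absent patient term: with a random patient intercept the SE stayed at 0.296 when the covariate was added. SAP 10.2 does mention mixed modelling in its imputation paragraphs. The second step as worded, however, is a fixed-effects model, and under either reading a main-effect covariate does not adjust the interaction.

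Third, exact invariance needs one value per patient. SAP 10.2.2 says baseline only for SVC; blood pressure and weight are measured repeatedly, and period-specific values would move the estimate.

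Fourth, no gain is shown for site, and a reason for dropping it could stand in the blacked-out entries of SAP section 13. The point on site is only the mismatch with the stratified design and the protocol model.

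Last, a one-record model drops any patient without a post-slope. This is probably minor: SAP 6.3 reports that the FAS and mFAS differ by one patient.

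**Conclusion.** The concern holds. The between-arm model leaves out the pre-slope as a covariate and the randomisation stratum, and patient-level main-effect covariates cannot adjust its estimate when pairs are complete. The last statement is algebra and needs no assumed values.

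The size of the precision loss does rest on assumed SDs and correlation: 63% more variance at Week 24 in the base case, 6% to about 230% over the range, and negligible power gain where measurement error is small and the true slopes are highly correlated. The direction was the same throughout. The change should be made, but the planned comparison is valid without it.

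**What to change.** For the between-arm comparison, use one record per patient and regress change in slope on treatment, pre-transplantation slope and site. Using post-slope as the response gives the identical treatment estimate. Fit the SAP 10.2.2 covariates in that model. If two rows are kept, enter them as covariate-by-period terms and add a patient term.

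Keep the pre-specified within-arm comparison as a paired test of each patient's slope change; do not take it from the adjusted model. Keep the unadjusted difference in change as a sensitivity analysis.

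The cost is SAP wording in 10.2 and 10.2.2 and about 3 degrees of freedom (one for pre-slope, two for site), with no new data. Expect less in the 10.2.1 subgroups defined by pre-transplantation decline in total score: the base-case Week 24 variance ratio is 1.30 (change below −2) and 1.19 (−2 or above), against 1.64 overall in the same simulation, assuming a mean decline of 1 point/month.
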